#### **Measurement of Treatment/Intervention Effect**

##### **Target Lesions & Target Lymph Nodes**

- **Measurable lesions** up to a maximum of 5 lesions representative of all involved organs, should be identified as “Target Lesions” and recorded and measured at baseline. These lesions can be non-nodal or nodal where no more than 2 lesions are from the same organ and no more than 2 malignant nodal lesions are selected.

**Note:** If fewer than 5 target lesions and target lymph nodes are identified (as there often will be), there is no reason to perform additional studies beyond those specified in the protocol to discover new lesions.

- **Target lesions and target lymph nodes** should be selected on the basis of their size, be representative of all involved sites of disease, but in addition should be those that lend themselves to reproducible repeated measurements. It may be the case that, on occasion, the largest lesion (or malignant lymph node) does not lend itself to reproducible measurements in which circumstance the next largest lesion (or malignant lymph node) which can be measured reproducibly should be selected.
- **Baseline Sum of Dimensions (BSD):** A sum of the longest diameter for all target lesions plus the sum of the short axis of all the target lymph nodes will be calculated and reported as the baseline sum of dimensions (BSD). The BSD will be used as reference to further characterize any objective tumor response in the measurable dimension of the disease.

- **Post-Baseline Sum of the Dimensions (PBSD):** A sum of the longest diameter for all target lesions plus the sum of the short axis of all the target lymph nodes will be calculated and reported as the post-baseline sum of dimensions (PBSD). If the radiologist is able to provide an actual measure for the target lesion (or target lymph node), that should be recorded, even if it is below 0.5 cm. If the target lesion (or target lymph node) is believed to be present and is faintly seen but too small to measure, a default value of 0.5 cm should be assigned. If it is the opinion of the radiologist that the target lesion or target lymph node has likely disappeared, the measurement should be recorded as 0 cm.
- **The minimum sum of the dimensions (MSD)** is the minimum of the BSD and the PBSD.

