**15.1.1. Response for Evaluation Criteria in Solid Tumors (RECIST) 1.1  
Criteria for Evaluating Response in Solid Tumors**

RECIST Version 1.1\* will be used in this study for assessment for tumor response.

\*As published in the European Journal of Cancer

**15.1.2. Response for Evaluation Criteria in Solid Tumors (RECIST) 1.1  
Criteria for Evaluating Response in Solid Tumors**

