### Evaluation of Target Lesions

- **Complete Response (CR):** All of the following must be true:
  - a. Disappearance of all target lesions.
  - b. Each target lymph node must have reduction in short axis to < 1.0 cm.
- **Partial Response (PR):** At least a 30% decrease in PBSD (sum of the longest diameter for all target lesions plus the sum of the short axis of all the target lymph nodes at current evaluation) taking as reference the BSD.
- **Progression (PD):** At least one of the following must be true:
  - a. At least one new malignant lesion, which also includes any lymph node that was normal at baseline (< 1.0 cm short axis) and increased to  $\geq$  1.0 cm short axis during follow-up.
  - b. At least a 20% increase in PBSD (sum of the longest diameter for all target lesions plus the sum of the short axis of all the target lymph nodes at current evaluation) taking as reference the MSD. In addition, the PBSD must also demonstrate an absolute increase of at least 0.5 cm from the MSD.

- **Stable Disease (SD):** Neither sufficient shrinkage to qualify for PR, nor sufficient increase to qualify for PD taking as reference the MSD.

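### As printed, the reference sum for target-lesion progression (MSD) uses no earlier scan, so regrowth after shrinkage is not progression until 120% of baseline

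*Combined protocol and SAP*

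**What the plan says.** Section 15.1.3 (Target Lesions & Target Lymph Nodes) names three sums: the baseline sum (BSD), the post-baseline sum (PBSD) and the minimum sum (MSD). It says that the MSD "is the minimum of the BSD and the PBSD". It does not tie PBSD to a particular visit.

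Section 15.1.4 (Evaluation of Target Lesions) then uses these sums:

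- Partial response is "At least a 30% decrease in PBSD" with the BSD as reference.
- Progression by target sum is "At least a 20% increase in PBSD". In that rule the PBSD is spelled out as the longest diameters plus "the short axis of all the target lymph nodes at current evaluation) taking as reference the MSD". The rule then sets a second, absolute condition on top of the relative one: "the PBSD must also demonstrate an absolute increase of at least 0.5 cm from the MSD".
- Stable disease is also judged against the MSD.

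Section 15.1.1 states that RECIST 1.1, as published, "will be used in this study for assessment for tumor response". The end of Section 15.1.4 refers the reader to the Statistical Considerations for formal definitions of analysis variables. Sections 19 and 20 define PFS but not the reference sum.

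**The concern.** A progression rule with a minimum as its reference should compare the current sum with the smallest sum seen earlier. The printed definition takes the minimum of two single quantities, and the rule that uses it makes one of them the current sum. Earlier post-baseline sums then drop out, and regrowth from a low point is not recognised while the sum stays below baseline.

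This bears on the primary endpoint, because PFS is dated by the first scan that documents progression (Section 15.1). The trial is open-label (Section 8.4), has about 10 sites (Synopsis), and scans are reviewed by the investigator or a designee (Section 3.3.1). No central review is described. Two readings of one sentence can therefore give different PFS dates for the same scan series, chosen by readers who know the arm. The same progression call opens cross-over from topotecan (Section 10.1), and the MSD also enters the stable-disease definition.

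**Working it through.** **The plan's own figure.** This point disputes no stated number. For reference, the power in Section 19.1 reproduces. With 86 events, HR 0.60, one-sided alpha 0.10 and 2:1 allocation, power = Φ(√(86 × 2/3 × 1/3) × |ln 0.60| − 1.2816) = Φ(4.372 × 0.5108 − 1.2816) = Φ(0.952) = 82.9%. With the stated event split (59 of 86 on pembrolizumab) it is 82.0%. The plan says about 82%. Neither power nor sample size depends on the MSD wording.

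**Inputs.** The MSD definition (15.1.3); the 20% and 0.5 cm thresholds and the PBSD at the current evaluation (15.1.4); imaging every 6 weeks (15.1). Let B be the baseline sum, C the current sum, and N the smallest sum at any earlier evaluation, baseline included.

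**Literal reading: MSD = min(B, C).**

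- If C ≤ B, then MSD = C. The increase is 0% and 0 cm, so the target-sum criterion cannot be met.
- If C > B, then MSD = B. Progression needs C ≥ max(1.2B, B + 0.5 cm).

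This is the rule that results from writing BSD in place of MSD. N appears nowhere.

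**Running-minimum reading: MSD = N.** Progression needs C ≥ max(1.2N, N + 0.5 cm).

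**Thresholds for B = 10 cm.** The literal threshold is always max(12.0, 10.5) = 12.0 cm.

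| Shrinkage at lowest sum | N (cm) | Running-minimum PD at (cm) | Literal PD at (cm) | Growth from N needed under the literal rule |
|---|---|---|---|---|
| 10% | 9.0 | 10.8 | 12.0 | 12/9 − 1 = 33% |
| 30% | 7.0 | 8.4 | 12.0 | 12/7 − 1 = 71% |
| 50% | 5.0 | 6.0 | 12.0 | 12/5 − 1 = 140% |
| 70% | 3.0 | 3.6 | 12.0 | 12/3 − 1 = 300% |

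The 10% row is stable disease, so the effect is not confined to responders.

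**One illustrative series.** Baseline 10 cm, then 7, 5, 6, 7.5, 9.5, 11.5 and 12.5 cm.

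- Running minimum: PD at the 3rd post-baseline scan (6 against 5 cm, +20% and +1.0 cm).
- Literal: that scan is still 40% below baseline, hence a partial response. The 6th scan is 11.5 against 10 cm (+15%), not PD. PD comes at the 7th (12.5 against 10 cm, +25%).
- Difference: 4 scans × 6 weeks = 24 weeks. The planned median PFS values are 12 and 20 weeks.

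**Range under an assumption that is not in the documents.** Suppose that the sum regrows by 20% to 50% per 6-week scan and nothing else ends PFS first. The literal rule then delays PD by 0–6 weeks after 10% shrinkage, 6–12 weeks after 30%, 12–24 weeks after 50%, and 18–42 weeks after 70%.

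**The case against.** **The definition can be read as a running minimum.** Section 15.1.3 does not confine PBSD to one visit. The qualifier about the current evaluation appears only in Section 15.1.4, where it may merely identify which sum is being tested. The literal reading also makes the MSD redundant with the BSD and tests a sum against a minimum that includes itself. This stands as evidence of intent: a baseline-referenced rule was almost certainly not meant. It does not correct the text, because no section refers to the smallest sum on study.

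**RECIST 1.1 governs.** It is named repeatedly and adopted as published, so sites may never apply the literal rule. That makes the harm conditional. But the protocol prints its own operational rule in its own terms, does not otherwise reproduce the published reference rule, and does not say which prevails if the two differ. Section 16.1.2 also cites irRC for removal from pembrolizumab where Section 16.2.1 cites RECIST 1.1. Those passages need reconciling in their own right.

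**Other routes to an event remain.** New lesions, unequivocal non-target progression and death end PFS whatever the target sum. This stands. The delays shown above apply only to patients whose first event would be target-sum growth.

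**A stronger reading that a reader might infer.** One could take the 32% and 12% response rates in Section 19.1, count 0.32 × 62 ≈ 20 pembrolizumab and 0.12 × 31 ≈ 4 topotecan patients as affected, and conclude that the rule biases the trial towards pembrolizumab by a calculable amount. The documents do not support that. Those rates are a power contrast for ORR and are not stated as forecasts for the two arms. The count omits stable-disease patients whose tumours shrank, and it includes responders who would progress by another route. The background rates (29% for pembrolizumab in a PD-L1-positive cohort, 14.1% for topotecan at 1.25 mg/m²) and the expectation of longer responses in Section 5.1.1 make that direction plausible. However, Section 3.1 also reports 24% for topotecan in sensitive relapse.

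**Conclusion.** Wrong as written. Taken together, Sections 15.1.3 and 15.1.4 define a reference sum that equals the smaller of baseline and current, so after any shrinkage the target-sum criterion is met only at 120% of baseline (or baseline plus 0.5 cm, if larger). With a 50% reduction from 10 cm, that is 12 cm instead of 6 cm.

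The threshold shift follows from the printed text alone. Three further statements are conditional:

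- Progression is dated late only where the literal rule is applied and no other event comes first.
- The resulting bias would favour the arm with more or deeper shrinkage. The documents do not establish which arm that will be.
- The size of any bias in the hazard ratio or in the chance of a positive test cannot be derived. It would need the depth of shrinkage, the regrowth rate, the share of patients who progress by target sum alone, and the share of readers applying the literal rule. None of these is given.

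It would go too far to say that PFS in this trial is biased, or that no site uses a nadir. What can be said is that the written rule for the primary endpoint, followed exactly, gives the wrong reference, and that differing readings by unblinded local readers are foreseeable.

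**What to change.** In Section 15.1.3, replace the MSD sentence with: *MSD is the smallest of the BSD and all PBSDs recorded at evaluations before the current one.* Align the progression and stable-disease wording in Section 15.1.4, so that the current sum is compared with this MSD, and tell sites of the change.

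The cost is a short text change. The sums are already recorded, no new data are needed, and sample size and power are unchanged.

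Optionally, recompute target-sum progression from the recorded sums and query disagreements with the investigator's call. This should be a consistency check only. Using it in place of the local reading would create a second source of progression dates and would need its own rules for discordant cases.

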### Non-Target Lesions & Non-Target Lymph Nodes

Non-measurable sites of disease are classified as non-target lesions or non-target lymph nodes and should also be recorded at baseline. These lesions and lymph nodes should be followed.

#### 15.1.4. Response Criteria

All target lesions and target lymph nodes followed by CT must be measured on re-evaluation at evaluation times specified in Section 15.2.1 & 15.2.3. Specifically, a change in objective status to either a PR or CR cannot be done without re-measuring target lesions and target lymph nodes.

Note: Non-target lesions and non-target lymph nodes should be evaluated at each assessment, especially in the case of first response or confirmation of response. In selected circumstances, certain non-target organs may be evaluated less frequently. For example, bone scans may need to be repeated only when complete response is identified in target disease or when progression in bone is suspected.

### Evaluation of Target Lesions

- **Complete Response (CR):** All of the following must be true:
  - a. Disappearance of all target lesions.
  - b. Each target lymph node must have reduction in short axis to < 1.0 cm.
- **Partial Response (PR):** At least a 30% decrease in PBSD (sum of the longest diameter for all target lesions plus the sum of the short axis of all the target lymph nodes at current evaluation) taking as reference the BSD.
- **Progression (PD):** At least one of the following must be true:
  - a. At least one new malignant lesion, which also includes any lymph node that was normal at baseline (< 1.0 cm short axis) and increased to  $\geq$  1.0 cm short axis during follow-up.
  - b. At least a 20% increase in PBSD (sum of the longest diameter for all target lesions plus the sum of the short axis of all the target lymph nodes at current evaluation) taking as reference the MSD. In addition, the PBSD must also demonstrate an absolute increase of at least 0.5 cm from the MSD.

- **Stable Disease (SD):** Neither sufficient shrinkage to qualify for PR, nor sufficient increase to qualify for PD taking as reference the MSD.

#### Evaluation of Non-Target Lesions & Non-target Lymph Nodes

- **Complete Response (CR):** All of the following must be true:
  - a. Disappearance of all non-target lesions.
  - b. Each non-target lymph node must have a reduction in short axis to <1.0 cm
- **Non-CR/Non-PD:** Persistence of one or more non-target lesions or non-target lymph nodes.
- **Progression (PD):** At least one of the following must be true:
  - a. At least one new malignant lesion, which also includes any lymph node that was normal at baseline (< 1.0 cm short axis) and increased to  $\geq 1.0$  cm short axis during follow-up.
  - b. Unequivocal progression of existing non-target lesions and non-target lymph nodes. (NOTE: Unequivocal progression should not normally trump target lesion and target lymph node status. It must be representative of overall disease status change.)

#### Overall Objective Status

The overall objective status for an evaluation is determined by combining the patient's status on target lesions, target lymph nodes, non-target lesions, non-target lymph nodes, and new disease as defined in the following tables:

#### For Patients with Measurable Disease

Table 11. Target and Non-Target Lesions

Target Lesions & Target Lymph Nodes	Non-Target Lesions & Non-Target Lymph Nodes	New Sites of Disease	Overall Objective Status
CR	CR	No	CR
CR	Non-CR/Non-PD	No	PR
PR	CR Non-CR/Non-PD	No	PR
CR/PR	Not All Evaluated	No	PR**
SD	CR Non-CR/Non-PD Not All Evaluated	No	SD
Not all Evaluated	CR Non-CR/Non-PD Not All Evaluated	No	Not Evaluated (NE)
PD	Unequivocal PD CR Non-CR/Non-PD Not All Evaluated	Yes or No	PD
CR/PR/SD/PD/Not all Evaluated	Unequivocal PD	Yes or No	PD

Target Lesions & Target Lymph Nodes	Non-Target Lesions & Non-Target Lymph Nodes	New Sites of Disease	Overall Objective Status
CR/PR/SD/PD/Not all Evaluated	CR Non-CR/Non-PD Not All Evaluated	Yes	PD

**Symptomatic Deterioration:** Patients with global deterioration of health status requiring discontinuation of treatment without objective evidence of disease progression at that time, and not either related to study treatment or other medical conditions, should be reported as PD due to “symptomatic deterioration.” Every effort should be made to document the objective progression even after discontinuation of treatment due to symptomatic deterioration.

#### Definitions of analysis variables

Formal definitions of variables used in analyses can be found in the Statistical Considerations section of the protocol.

### 16. END OF TREATMENT/INTERVENTION

#### 16.1. DURATION OF TREATMENT

##### 16.1.1. CR, PR or SD

Patients who are in CR, PR or SD will continue on therapy per the study calendar. After treatment is discontinued, patients will be followed per the study calendar

##### 16.1.2. Disease Progression

Remove from protocol therapy any patient with disease progression by irRC while receiving pembrolizumab (MK-3475) document details, including tumor measurements, on data forms. After disease progression, patients should be followed for survival per the study calendar (Section 9).

##### 16.1.3. Discontinuation of Study Agent

If the patient discontinues pembrolizumab (MK-3475) patients should be followed for survival per the study calendar (Section 9).

#### 16.2. PATIENT WITHDRAWAL/DISCONTINUATION CRITERIA

##### 16.2.1. Patient Withdrawal

In the absence of serious toxicity or complications, all patients will continue treatment until evidence of disease progression, or for up to 24 months, whichever is first.

Patients may withdraw consent at any time for any reason or be dropped from the study at the discretion of the investigator should any untoward effect occur. In addition, a patient may be withdrawn by the investigator or the Sponsor if enrollment into the study is inappropriate, the study plan is violated, or for administrative and/or other safety reasons. If, at any time the constraints of this protocol are detrimental to the patient's health and/or the

patient no longer wishes to continue protocol therapy, protocol therapy shall be discontinued.

A patient must be discontinued from the study for any of the following reasons:

- The patient or legal representative (such as a parent or legal guardian) withdraws consent.
- Confirmed radiographic disease progression while receiving pembrolizumab as per RECIST 1.1.  
*Note:* A patient may be granted an exception to continue on treatment with confirmed radiographic progression if clinically stable or clinically improved, per the investigator's discretion, given the potential of tumor flare.
- Unacceptable adverse experiences
- Intercurrent illness that prevents further administration of treatment
- Investigator's decision to withdraw the patient
- The patient has a confirmed positive serum pregnancy test
- Noncompliance with study treatment or procedure requirements
- The patient is lost to follow-up
- Administrative reasons

The End of Treatment and Follow-up visit procedures are listed in Section 9. After the end of treatment, each patient will be followed for a minimum of 30 days for adverse event monitoring. Serious adverse events will be collected for up to 90 days after the end of treatment or 30 days after the end of treatment if the subject initiates new anticancer therapy, whichever is earlier. Patients who discontinue for reasons other than progressive disease will have post-treatment follow-up for disease status every 6 weeks until disease progression, initiating a non-study cancer treatment, withdrawing consent or becoming lost to follow-up. After documented disease progression each patient will be followed by telephone every 12 weeks for overall survival until death, withdrawal of consent, or the end of the study, whichever occurs first.

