**1. SYNOPSIS****1.1. STUDY SUMMARY**

Abbreviated Title	Pembrolizumab vs Topotecan in the Second-line Treatment of Patients with Small Cell Lung Cancer
Study Phase	Randomized Phase II
Clinical Indication	Small cell lung cancer (SCLC) patients in need of second-line therapy after standard platinum/etoposide chemotherapy.
Study Type	Interventional
Type of Control	Active control without placebo
Route of Administration	Intravenous
Study Blinding	Unblinded open-label
Treatment Groups	Topotecan every 3 weeks until progression of disease; at which point, patients can cross over to the pembrolizumab arm.  Pembrolizumab 200mg every 3 weeks until progression of disease or up to 24 months, whichever occurs first.
Number of Study Patients	Approximately 98 patients will be enrolled at an anticipated 10 sites.
Estimated Duration of Study	Approximately 19 to 23 months to accrue and enroll the patients, with an additional 6 months of follow-up to observe events for the primary endpoint of progression free survival after the last patient is started on study; we have included an additional 6 months to allow patients responding on study drug to remain on protocol.
Subject Eligibility	Patients with sensitive or refractory disease will be eligible for the study; where sensitive disease will be defined as those patients with disease progression after treatment with standard first-line etoposide/platinum $\geq 60$ days from completing chemotherapy, and refractory disease will be defined as patients with disease progression $< 60$ days from completing chemotherapy. Patients with treated brain metastases will be eligible. Patients with underlying or previous paraneoplastic syndromes are not eligible.
Study Objectives	The primary endpoint is to determine if there is an improvement in progression free survival for SCLC patients treated with pembrolizumab compared to topotecan. RECIST 1.1 will be used for this analysis.  Secondary endpoints will include safety, objective response rate by RECIST 1.1, and overall survival. Exploratory endpoints based on correlative studies will be assessed.

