Study Design	This is a multi-institutional, randomized, open-label phase II study of pembrolizumab compared to topotecan, administered to patients with SCLC who have progressed or relapsed after first-line treatment with etoposide and platinum. Patients will be randomized in a 2:1 fashion to receive pembrolizumab or topotecan. Participants in the topotecan arm that progress will be allowed to cross-over to the pembrolizumab arm.
Study Treatment Plan	Pembrolizumab Arm: Pembrolizumab will be administered via IV infusion at 200 mg every 3 weeks, and treatment continued for up to 24 months, until documented disease progression, unacceptable side effects or intercurrent illness that prevents further administration of treatment, investigators' decision to

	
withdraw the subject, subject withdraws consent, pregnancy of the patient, noncompliance of the patient, or for administrative reasons.
 
Topotecan Arm: Topotecan will be administered via IV infusion at 1.25 mg/m^2 on days 1 to 5 of a 3-week cycle. Pegfilgrastim may be given on day 6, 7, or 8 to offset neutropenia. Patients who progress in the topotecan arm will be allowed to cross-over to the pembrolizumab arm.

Efficacy Assessments	
Patients will be evaluated every 6 weeks (42 ± 7 days) with radiographic imaging to assess response to treatment. Investigators will make all treatment-based decisions using RECIST 1.1.

Safety Assessments	
Patients will be evaluated clinically by physical exam and with routine blood work every 21 days. Adverse events will be monitored throughout the Study and graded in severity according to the guidelines outlined in the NCI Common Terminology Criteria for Adverse Events (CTCAE) version 4.

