-  Patients who discontinue study treatment for a reason other than disease progression will move into the Follow-up Phase and should be assessed every 6 weeks ( $42 \pm 7$  days) by radiologic imaging to monitor disease status, development of drug related SAEs and ECIs/irAEs, and initiation of a new antineoplastic therapy. Follow-up visit 1 should be scheduled 6 weeks after the last dose of study treatment. Unless otherwise noted in the flow chart, every effort should be made to collect patient information until the start of new antineoplastic therapy, disease progression, or death, whichever comes first.
-  Once a patient experiences disease progression or starts a new antineoplastic therapy, the patient moves into the Survival Follow-up Phase and should be contacted by telephone every 3 months to assess for survival status, development of drug related SAEs and ECIs/irAEs and the start of new antineoplastic therapy if applicable.
-  Record all AEs occurring within 30 days after the last dose of study treatment or until initiation of a new antineoplastic therapy, whichever comes first. Report all SAEs (related and unrelated to study treatment) occurring within 90 days of the last dose of study treatment or the start of new anti-cancer treatment, whichever comes first. All ECIs/irAEs occurring within 90 days of the last dose of study treatment should be reported regardless of initiating new anticancer therapy. After this time, report only SAEs and ECIs/irAEs that are considered related to study treatment.
-  If archival sample is not available, fresh tissue samples will be collected for correlative studies.
-  Those patients receiving pembrolizumab will undergo a biopsy obtained during week 4 to 6 of treatment for biomarker analysis, if clinically feasible and safe. A tumor lesion not previously radiated (required for PD-L1 determination) should be biopsied. The tumor sample must be sent to the AFT-Biorepository. See AFT 1 Correlative Science Manual for additional details.
-  Patients on the topotecan arm who progress and are to cross-over to the pembrolizumab arm, will undergo a biopsy just before initiating experimental treatment, if clinically feasible and safe. A tumor lesion not previously radiated (required for PD-L1 determination) should be biopsied. The tumor sample must be sent to the AFT-Biorepository.

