#### **Experimental Arm**

**Pembrolizumab:** 200 mg IV every 21-days until progression of disease or unacceptable toxicities.

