#### 15.1. SCHEDULE OF EVALUATIONS

The initial tumor imaging will be performed within 14 days prior to the first dose of study treatment. Scans performed as part of routine clinical management are acceptable for use as the screening scan if they are of diagnostic quality and performed within 14 days prior to the first dose of study treatment. On-study imaging will be performed every 6 weeks ( $42 \pm 7$  days) after the first dose of study treatment or more frequently if clinically indicated. The timing for imaging studies should **follow calendar days** and should not be adjusted for delays in cycle starts or extension of topotecan or pembrolizumab (MK-3475) cycle frequencies. The same imaging technique should be used in a patient throughout the study.

After the first documentation of progression while receiving pembrolizumab (MK-3475) alone it is at the discretion of the investigator to keep a clinically stable patient on study treatment or to stop study treatment until repeat imaging performed 4-6 weeks later confirms progression.

Clinical stability in a patient whose disease displays radiographic progression is defined as:

- Absence of symptoms and signs indicating clinically significant progression of disease (including worsening laboratory values).
- NO decline in ECOG performance status.
- Absence of rapid progression of disease or progressive tumor at critical anatomical sites (e.g. cord compression) requiring urgent alternative medical intervention.

Patients that are deemed clinically unstable are not required to have repeat imaging for confirmation. Upon repeat imaging, if progression is confirmed, then the patient will be discontinued from study treatment. As the primary endpoint is PFS, the date of the first scan that documented progression should be used. If progression is not confirmed, then the patient should resume/continue study treatment and have the next scan according to the every 6-week ( $42 \pm 7$  days) schedule from the first dose of study treatment. When feasible, patients should not be discontinued until progression is confirmed.

For patients who discontinue study treatment for reasons other than disease progression, imaging should continue according to the same schedule (every 6 weeks/ 42 ± 7 days) until the patient experiences confirmed disease progression or starts a new antineoplastic therapy.

Study eligibility will be according to RECIST 1.1 criteria.

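### The protocol gives incompatible instructions on stopping pembrolizumab at progression: Sections 15.1, 16.1.2 and 16.2.1 cannot all be followed for the same patient

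*Combined protocol and SAP*

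**What the plan says.** The instructions for pembrolizumab at progression are spread over several sections.

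- **Section 1.1 (synopsis).** The treatment groups row gives "Pembrolizumab 200mg every 3 weeks until progression of disease or up to 24 months, whichever occurs first". The treatment plan row gives "treatment continued for up to 24 months, until documented disease progression, unacceptable side effects". The schema in Section 1.2 also stops treatment at progression on pembrolizumab, within a 24-month limit.
- **Sections 3.3.2 and 10.1.** Section 3.3.2 treats until documented progression and has investigators base treatment decisions on RECIST 1.1, as does Section 1.1. Section 10.1 reads "200 mg IV every 21-days until progression of disease or unacceptable toxicities". Neither mentions confirmation.
- **Section 15.1.** After a first progressive scan on pembrolizumab, "it is at the discretion of the investigator to keep a clinically stable patient on study treatment or to stop study treatment until repeat imaging" 4 to 6 weeks later settles the matter. Then: "Upon repeat imaging, if progression is confirmed, then the patient will be discontinued from study treatment". The section also fixes the PFS date at the first scan that documented progression.
- **Section 16.1.2.** Patients on pembrolizumab come off protocol therapy at progression by irRC.
- **Section 16.2.1.** It opens with "all patients will continue treatment until evidence of disease progression, or for up to 24 months, whichever is first". Confirmed RECIST 1.1 progression then appears in a list of reasons for which a patient must be discontinued, followed by a note: "A patient may be granted an exception to continue on treatment with confirmed radiographic progression if clinically stable or clinically improved", at the investigator's discretion.
- **Follow-up.** Table 2 footnote 21 says "Once a patient experiences disease progression or starts a new antineoplastic therapy, the patient moves into the Survival Follow-up Phase", with telephone contact every 3 months. The closing paragraph of Section 16.2.1 likewise prescribes telephone contact after documented progression. Section 16.3 defines survival-only follow-up as a period in which the participant no longer receives study treatment.

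**The concern.** A site with a clinically stable patient whose progression has just been confirmed finds one section that requires stopping and another that allows continuing. A third section applies a different response criterion. Section 21.9 says that deviation waivers are not granted, so a site that uses the note in Section 16.2.1 could be recorded as deviating from Section 15.1.

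What is at stake is how long pembrolizumab is given after progression. The adverse-event and serious-adverse-event collection windows run from the last dose or the end of treatment, so they move with it. So does the time at which a patient becomes available for next-line therapy. The discretion in Sections 15.1 and 16.2.1 is written only for pembrolizumab, in an open-label trial that compares adverse-event percentages between arms. Any site variation therefore falls on arm E and on arm C patients who have crossed over.

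**Working it through.** **1. The rules side by side**

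| Section | First progressive scan | Confirmed progression | Criterion |
|---|---|---|---|
| 1.1, 1.2, 3.3.2, 10.1 | Stop; no confirmation step | Not addressed | RECIST 1.1 for treatment decisions (1.1, 3.3.2) |
| 15.1 | Clinically stable: continue or pause at investigator discretion | Stop; no exception | RECIST 1.1 |
| 16.1.2 | Stop at progression | Not addressed | irRC |
| 16.2.1, opening | Stop at evidence of progression | Not addressed | Not stated |
| 16.2.1, list and note | Not addressed | Must stop, but may continue if clinically stable or improved | RECIST 1.1 |

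At confirmed progression, Section 15.1 and the note in 16.2.1 give opposite answers for the same clinically stable patient. Neither cites the other. Section 16.1.2 conflicts with the RECIST 1.1 basis on a separate axis, so settling 15.1 against 16.2.1 would not remove it.

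**2. Doses between first progression and confirmation**

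Inputs: one dose every 21 days, and a confirmatory scan 28 to 42 days after the first (28 days is the earliest in Table 2 footnote 17; 4 to 6 weeks in Section 15.1). Assume no dose delays, and do not count doses given on a scan day. Let the next dose fall *d* days after the first progressive scan, with *d* from 1 to 21, and the following one at *d* + 21.

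- 28-day gap: two doses if *d* ≤ 6, since *d* + 21 ≤ 27; otherwise one.
- 42-day gap: two doses if *d* ≤ 20, since *d* + 21 ≤ 41; one if *d* = 21.

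A patient treated through to confirmation gets 1 to 2 doses, and a patient stopped or paused at the first scan gets 0. The range is 0 to 2. Each extra dose moves the last-dose date by 21 days, so the windows shift by 0 to 42 days up to confirmation. Beyond confirmation, the exception is limited only by the overall cap: 24 months in Sections 1.1 and 16.2.1, and 1 year for crossover patients in Section 10.1.

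**3. How many patients could be affected in arm E**

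Section 19.1 states 59 arm E events at the final analysis. Its own inputs give a somewhat lower figure:

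- Hazard: ln 2 / 20 = 0.03466 per week.
- Accrual: 93 / 4 = 23.25 months, about 101 weeks, taken as uniform. Further follow-up: 26 weeks.
- P(event) = 1 − exp(−0.03466 × 26) × [1 − exp(−0.03466 × 101)] / (0.03466 × 101) = 1 − 0.4061 × 0.9698 / 3.500 = 0.8875.
- Expected events: 62 × 0.8875 = 55.0.

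This does not reproduce the stated 59, but nothing here rests on the difference. Either number is only an upper bound. It counts deaths without progression, and it counts clinically unstable patients, who have no option to continue under Section 15.1. Arm C patients who cross over and then progress on pembrolizumab come on top.

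**4. Follow-up text**

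A patient treated past a first or confirmed progression meets footnote 21's trigger for survival follow-up but does not meet Section 16.3's definition of it. Footnote 17 also requires repeat imaging after first progression if the patient is clinically stable, whereas the survival follow-up column of Table 2 has no imaging.

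**The case against.** The strongest reply is that most of this is summary wording against detail. The synopsis and schema close by referring the reader to the full protocol text. Sections 3.3.2 and 10.1 simply say progression, and Section 15.1 can be read as the operational detail, supported by footnote 17. A mandatory list with an explicit note is a rule with an exception, not a contradiction in itself. Section 15.1 gives discretion on purpose, so some variation in exposure is intended and would remain after any rewording. The safety windows move with the last dose by design.

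Much of that stands, and the synopsis alone would not carry the point. It does not remove the conflict between Sections 15.1 and 16.2.1. Both are detailed operative sections, and 15.1 leaves no room for the exception that 16.2.1 grants. Nor does it explain the irRC criterion in 16.1.2.

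A reader might infer from footnote 21 that patients still being dosed drop out of scheduled safety assessment. The documents do not support that. Section 16.3 limits survival-only follow-up to participants off study treatment, and Table 2 places it under post-treatment evaluations. The text under Table 3 requires acceptable laboratory results before each dose. Crossover patients, who have by definition progressed, repeat the assessments from study start apart from the week 4 to 6 biopsy. Footnote 21 is misaligned, but it does not by itself end monitoring.

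A reader might also infer that the primary endpoint is compromised. Section 15.1 answers this: the event date is the first scan that documented progression, however long treatment then continues.

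**Conclusion.** The point stands as a conflict in operative text that should be corrected. Sections 15.1 and 16.2.1 give opposite instructions at confirmed progression, Section 16.1.2 uses another criterion, and the follow-up text does not fit patients treated past progression.

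Per patient, the effect is about 0 to 2 doses (0 to 42 days) up to confirmation. Under the exception it is then open-ended within the treatment cap. This assumes undelayed 3-weekly dosing and a confirmatory scan 28 to 42 days after the first.

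It would be tempting to say that some 55 arm E patients are affected. The documents do not allow that: 55 is the expected number of all arm E PFS events under exponential times and uniform accrual, and the number of progressing patients who are stable enough to continue is unknown. It would also be tempting to claim a bias in overall survival between arms. Crossover patients fall under the same rules as arm E, and the documents give no basis for a direction or size. The supported conclusion is site-dependent exposure after progression, with consequences for adverse-event collection and next-line timing.

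**What to change.** Reconcile Sections 1.1, 1.2, 3.3.2, 10.1, 15.1, 16.1.2 and 16.2.1 into one statement of what happens to pembrolizumab at first progression and at confirmed progression, under one named response criterion. It should say explicitly whether the exception in 16.2.1 exists. Have the other sections refer to that statement. Which rule and which criterion to keep is the sponsor's decision.

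Align Table 2 footnote 21 and the closing paragraph of Section 16.2.1 with the definition of survival-only follow-up in Section 16.3. Keep footnote 21's existing trigger for patients who start a new antineoplastic therapy.

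If treatment past progression is retained, a descriptive count of doses given after progression would help in reading the safety tables; this is optional.

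The cost is amendment wording and, if wanted, one descriptive count. Sample size, the PFS definition and the primary analysis do not change.
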